Do-MoST introduces the Decision Aid when MI has readied patients to make decisions about help. Decision aids have been used by providers and patients to make decisions together using the best available evidence; they encourage patients to consider available treatment options and the likely benefits and harms of each. Providers, such as decision coaches (trained to support patient involvement in decisions), help patients become well-informed and develop personal preferences for available options, and offer professional guidance. Deciding about treatment options is a dynamic process, with information exchange between health care staff and patients. Historically, most Decision Aids have been employed in situations without a clear, “best” treatment option; instead, the goal is to help patients make decisions that are satisfying to them. In the case of medical-surgical inpatients with AUD, evidence is clear that outcomes would likely be better if the individual reduced alcohol consumption with treatment engagement. DO-MoST, capitalizing on patients’ motivation to change, will share this evidence with patients, but discussions will focus on choosing the help option that is best from the patient’s perspective. Existing empirically-based options for AUD include medication treatments (3 types: disulfiram, acamprosate, and naltrexone, approved by the FDA), behavioral treatments (4 types: cognitive-behavioral, motivational enhancement, behavioral couples, and twelve-step facilitation therapy, which are equivalent in terms of outcomes), and mutual-help groups. The goal of the Decision Aid component is to present AUD patients with the pros and cons of each option and engage them in a discussion of which option might be best for them if they choose to pursue some form of help.

A Decision Aid for AUD treatment may be particularly effective because individuals with AUD are often unaware of the range of available options in terms of treatment modality and outcomes. Even Veterans receiving detoxification and other psychiatry services for their substance use disorders are unaware of the range of evidence-based treatment options available for AUDs, such as pharmacotherapy or outpatient treatment. Patients often believe that the 28-day residential treatment model is the main one available and recommended. Further, patients often do not view providers as open to discussion of the goal of cutting

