Number and length of the project's in-person and phone sessions will not be matched between conditions. An important component of DO-MoST is its supportive nature, apart from specific content. It would be quite difficult to match time and attention DO-MoST and UC groups receive without also equating support. **UC.** All patients, regardless of condition, will receive usual inpatient care at the Palo Alto or Ann Arbor VA. At both sites, implementation of ORYX measures requires that, under usual care, when a patient screens positive on the AUDIT-C administered at intake, a provider (social worker, nurse) provides BI, i.e., tells the patient that problems are associated with alcohol use, and about recommended drinking limits; notes the patient as ready to change drinking or not, and as agreeing to treatment or not. If the patient agrees to treatment, specialty addiction services are notified. Both sites have addiction outpatient and residential specialty care offering behavioral therapies (the 4 targeted in this study), pharmacotherapy (the 3 targeted in this study), and 12-step meetings, and Patient Aligned Care Teams within primary care.

**DO-MoST.** Patients assigned to the DO-MoST condition will receive usual care plus the DO-MoST intervention. They will attend one 50-minute individual session during their inpatient stay with a Decision Coach (a trained clinical provider, e.g., MSW). Patients in DO-MoST will also attend 6 biweekly 15-minute telephone sessions from the same Decision Coach. In our current HSR&D project with detox inpatients, 100% of patients completing a baseline interview also participated in the inpatient session with the TeleCoach.

At the initial session, the Decision Coach and patient will engage in MI to discuss the patient's medical condition and need to make decisions about drinking goals, and their benefits and adverse effects, i.e., abstinence vs. moderation vs. no change. MI components include empathy when giving personalized feedback (Engage); conveying the patient's responsibility for change (Focus); and support of the patient's self-efficacy to make changes (Evoke, Plan). MI includes reviewing patients' values (e.g., good health and relationships) and substance use patterns and their consequences. The discrepancy between patients' substance use and ability

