**Help utilization.** We will use the TLFB to assess patients' use of VA and non-VA help for alcohol and drug use (type and amount of pharmacotherapies, behavioral treatments, mutual-help groups), including setting (inpatient, residential, outpatient, primary care, e.g., BIs). Primary outcomes for alcohol are any help use (yes/no for initiation) and duration of use (engagement). The primary outcome for engagement will be duration (not completion) of treatment because the duration and continuity of care are more closely related to outcomes than is treatment completion; and our operations partners stated that in light of adaptive treatments, treatment completion is not cut-and-dried among AUD patients, such that duration is more reliable and meaningful. In addition, recommendations (e.g., from NIH) are that help be obtained for at least 1-2 years when beginning recovery from AUD; such sustained help is needed to "retrain brains" affected by chronic alcohol use. We will also use the Addiction Severity Index (ASI) to assess the participant's VA and non-VA history of lifetime treatment use including addiction, mental health, and medical-surgical care (outpatient, inpatient, residential, emergency). Data on non-VA health services use will be collected at baseline and follow-ups to help determine whether the two condition arms are balanced and ensure that any observed changes in VHA services use are not due simply to changes in non-VA care.

Related functioning. We will use selected portions of the ASI to fill in information missing from the TLFB and Veterans SF-12. The ASI, used to monitor VHA addiction patients' outcomes systemwide and in our projects, is a structured, clinical research interview that assesses 4 problem areas in addition to substance use and medical status: psychiatric, family/social, legal, and employment. In each area, a composite score is produced from items that are standardized and summed to provide an internally consistent evaluation of patient status in the past 30 days. Scores range from 0 to 1, with higher scores indicating poorer outcomes.

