B.3.7 During-treatment assessments. The start-up period in which Decision Coaches are trained will be important to establishing the fidelity with which DO-MoST is delivered. To assess the integrity of the DO-MoST condition throughout the study, sessions will be evaluated against a protocol checklist (adapted from Drs. [name] and [name]'s Decision Aid studies, and from the PIs' previous and ongoing MI-TM studies with psychiatry and detox inpatients). All phone sessions will be audiotaped (with appropriate consent). Phone sessions will be evaluated by [name] (assisted by the PIs) under the following schedule: (1) the first 15 phone calls for each Decision Coach will be assessed for protocol fidelity, and the Coach will be provided corrective feedback, and (2) eight calls will be reviewed at random each month to ensure ongoing fidelity of the intervention. No problems with adherence or responding appropriately to feedback were noted previously.

B.3.8 Follow-up assessments. Patients' follow-up data will come from administrative data in the VA Corporate Data Warehouse (CDW), and patient self-report. CDW data will cover behavioral health provided within primary care and addiction specialty care encounters, i.e., entry into addiction treatment, and types, timings, and durations of treatments. Self-report data will include drinking and help preferences; use of alcohol (and other drugs); medical status; help participation; other functioning; and potential explanatory mechanisms linking help to outcomes, i.e., motivation, commitment, and self-efficacy to change alcohol-related behaviors; decisional conflict about help.

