The TLFB will also be used to measure self-reported VA and non-VA alcohol-related, mental health, and medical help (treatment types, amounts, and settings) since the previous interview. Primary outcomes will be any use of alcohol help, and duration (weeks) of help. The ASI's selected portions on functioning will produce psychiatric, family/social, legal, and employment composite scores, and assess housing status. We will use measures used at baseline to assess motivation to change alcohol use, commitment to abstinence, self-efficacy to resist drinking, and Decisional Conflict with regard to drinking help options at follow-ups.

B.3.9 Procedures to Locate and Follow Patients. To ensure high follow-up rates, we will adhere to well-established procedures for locating and following substance use disorder, psychiatry, and medical patients in longitudinal studies. We have extensive experience in retaining research participants using proactive retention strategies, tracking protocols, and interviewer training procedures. Our Centers have conducted long-term studies with extremely high follow-up rates, e.g., 80% among individuals with AUDs followed for 16 years, 80% among depressed patients and controls followed for 23 years; 92% for addiction patients at 1 year, and 84% for dual diagnosis patients at 2 years. Our retention strategies include (1) research assistant interviewers are comfortable with the population under study and trained to establish rapport, (2) maintain toll-free telephone numbers for participants to report contact information changes (especially useful for patients who may lose their ongoing access to a telephone during the study), (3) obtain and verify in-depth locator and tracking information at intake, and update records at each interview and between interviews, (4) maintain consistent contact between interviews (e.g., thank you cards to enhance rapport and verify addresses), (5) keep detailed records of every contact and contact attempt, and (6) use the internet for tracking (e.g., Department of Corrections websites). We will use these procedures to target follow-up rates of at least 70%.

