B.3.11 Analysis Plan: Overview. In the RCT (Aim 2), primary hypotheses are that patients in DO-MoST, compared to those in UC, will be more likely to (1) enter addiction treatment or mutual-help (initiate), and attend it for a longer duration (engage); (2) have better alcohol use and medical outcomes; and (3) have fewer and delayed (greater number of days until) acute care episodes. To address these hypotheses, preliminary to regression modeling, we will check the distribution of the outcome and predictor variables, detect and adjust for missing data, and examine the baseline equivalence of the DO-MoST and UC groups. We will then evaluate the effect of the DO-MoST intervention on primary (addiction help utilization, alcohol and medical outcomes, acute care utilization) as well as secondary related outcomes, using generalized mixed-effects regression models (GLMM) appropriate for the distribution of the outcome variable and error term, and examine mechanisms of effects (the reasons DO-MoST is effective, and for whom).

Compare DO-MoST and UC conditions. We will use GLMM regression analyses to compare the UC with the DO-MoST condition on help utilization (e.g., any, and duration of, alcohol help; type of help), alcohol outcomes

(e.g., abstinence, percent of heavy drinking days), medical status, and related outcomes, and acute care utilization (rehospitalization, emergency department visits) over the 1-year follow-up period. Advantages of GLMM regression are that it permits regression modeling of repeated-measures data; does not require that all participants be measured at all time points to be included in analyses; and applies to continuous, dichotomous (e.g., any addiction help, abstinence, hospitalization), and Poisson-distributed outcomes (e.g., number of outpatient visits or inpatient days).

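### The primary help outcome (H1) has no single definition: as written it can count brief interventions, and no rule keeps Decision Coach contacts out of the count

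*Combined protocol and SAP*

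**What the plan says.** **Outcome definition.** Under Help utilization in B.3.6, the TLFB records type and amount of help from VA and non-VA sources, "including setting (inpatient, residential, outpatient, primary care, e.g., BIs"). The text continues: "Primary outcomes for alcohol are any help use (yes/no for initiation) and duration of use (engagement"). For follow-up, B.3.8 repeats this: "Primary outcomes will be any use of alcohol help, and duration (weeks) of help". The recall window there is "self-reported VA and non-VA alcohol-related, mental health, and medical help (treatment types, amounts, and settings) since the previous interview".

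**Hypothesis.** In B.3.11, H1 is that DO-MoST patients will be more likely to "enter addiction treatment or mutual-help (initiate), and attend it for a longer duration (engage"). A.5 likewise describes help as evidence-based treatment or mutual-help groups.

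**Brief interventions.** Under usual care (B.3.4), which both arms receive, after a positive AUDIT-C at intake "a provider (social worker, nurse) provides BI". Section A.4 says BIs lack efficacy in hospitalized patients with AUD. A.6 adds that, in medical settings, they do not increase receipt of alcohol services.

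**The intervention.** DO-MoST is one 50-minute inpatient session and six 15-minute biweekly calls with a trained clinical provider using motivational interviewing (B.3.4). A.5 lists the existing evidence-based options, among them "behavioral treatments (4 types: cognitive-behavioral, motivational enhancement, behavioral couples, and twelve-step facilitation therapy").

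**Administrative data.** B.3.8 states that "CDW data will cover behavioral health provided within primary care and addiction specialty care encounters". B.3.10 identifies the primary-care part by procedure codes and does not set BIs apart.

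**The concern.** Two kinds of contact that are not the help H1 is about could enter the H1 count, and they act in opposite directions.

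- **Brief interventions** can occur in either arm. If they count, patients in both arms register as initiators for a contact that the plan itself regards as ineffective, and a real difference shrinks.
- **Decision Coach contacts** occur in the DO-MoST arm only. A patient who is asked about alcohol help since the last interview may well mention regular calls with a clinician about drinking. If these are coded as behavioural treatment, initiation and weeks of help rise in that arm alone.

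The mediation analysis in B.3.12 uses help initiation and duration as mediators. If the mediator includes intervention contacts, part of the path from DO-MoST to help is the intervention predicting itself.

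**Working it through.** **1. The sections side by side.**

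| Section | What counts as help |
|---|---|
| B.3.6 | any help use, all settings, primary-care BIs named as an example |
| B.3.8 | any alcohol help, and weeks of help, since the previous interview |
| B.3.11 (H1) | addiction treatment or mutual-help |
| A.5 | evidence-based treatment or mutual-help groups |

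B.3.6 admits a contact that B.3.11 and A.5 do not. No section sets a minimum content for help or removes BIs or coach contacts.

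**2. Timing.** The calls run for 12 weeks. The first follow-up is at 3 months, on completion of the intervention, and its TLFB reaches back to the baseline interview, so its window spans the calls. The usual-care BI follows the AUDIT-C at admission, while the baseline interview takes place later in the same stay. The order of BI and baseline is not stated, so that BI may fall before the window. BIs in primary care after discharge, or at a readmission, fall inside it.

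**3. Illustration for coach contacts, with no true effect.** The plan gives no figure for this outcome that could be reproduced. Inputs:

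- 78 per arm (B.3.1) and a follow-up target of at least 70% (B.3.9): 0.70 × 78 = 54.6, taken as 54 per arm.
- True initiation p, equal in both arms: 18% or 43%. Both are borrowed from A.4 (attendance at a placement evaluation among older inpatients, and treatment entry in a pilot referral program). Neither is a planning rate for this trial.
- Share f of otherwise-none DO-MoST patients counted as initiators because of coach contacts: 5%, 10% or 20%. This is assumed; the documents give no rate.
- Two-sided 5% test, assumed because the plan states no alpha.

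Apparent DO-MoST rate: q = p + (1 − p)f. With m = (p + q)/2, s0 = √[2m(1 − m)/54] and s1 = √{[p(1 − p) + q(1 − q)]/54}, the chance of significance is Φ[(q − p − 1.96·s0)/s1] + Φ[(−(q − p) − 1.96·s0)/s1].

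Example, p = 0.18 and f = 0.10: q = 0.18 + 0.82 × 0.10 = 0.262; m = 0.221; s0 = 0.0799; s1 = 0.0795. The first term is Φ[(0.082 − 0.1566)/0.0795] = Φ(−0.94) = 0.174; the second is about 0.001. The sum is about 0.18.

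| f | p = 18%: q | significant | p = 43%: q | significant |
|---|---|---|---|---|
| 5% | 22.1% | 8% | 45.9% | 6% |
| 10% | 26.2% | 18% | 48.7% | 9% |
| 20% | 34.4% | 49% | 54.4% | 22% |

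The nominal value is 5% throughout.

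**4. Duration.** If a share f of the DO-MoST arm is credited with w extra weeks, the arm mean rises by f × w. With w = 6 (one week per call) to 12 (the whole span), f = 10% adds 0.6 to 1.2 weeks and f = 20% adds 1.2 to 2.4 weeks.

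**5. Illustration for BIs.** Take a true difference of 18% against 40.3% (Cohen's h = 0.5, chosen to match the plan's 0.50) and 54 per arm. Power is 73% with no BIs counted. If a BI is recorded for 25% of patients in each arm, the rates become 1 − 0.82 × 0.75 = 38.5% and 1 − 0.597 × 0.75 = 55.3%, and power falls to 41%. At 50% it is 23%. These shares are also assumed.

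**The case against.** The strongest reply is that the plan's intent is plain. DO-MoST leads to help (A.5), the calls support starting help and staying with it (B.3.4), and B.3.12 treats calls as dose and help as mediator. A reader might infer from the missing exclusion that DO-MoST must win on H1 by construction. The documents do not support that: the bias arises only if patients report coach calls as treatment and staff code them so. Motivational enhancement appears in A.5 as a treatment option, not in a coding list, and nothing says that coach calls create encounters in the Corporate Data Warehouse (CDW). What remains is that intent is not a coding rule, and blinded interviewers (B.3.8) cannot be relied on to recognise and discard these calls.

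A reader might also infer that every usual-care patient scores as an initiator through the inpatient BI. That does not follow either. The BI named in B.3.6 is a primary-care one, and the index-stay BI may precede the outcome window.

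B.3.6 does already record type, amount and setting, so much of the raw information will exist. What is missing is the rule that derives the outcome from it.

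Finally, the percentages rest on assumed misreporting rates and one two-proportion test. The plan uses a mixed model over four time points, and coach calls fall essentially in the first follow-up interval. That objection stands, so the figures show direction and sensitivity only.

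**Conclusion.** The concern holds as a conflicting and incomplete outcome definition. B.3.6 and B.3.8 allow a BI to count as initiation, which H1 in B.3.11 and the background do not, and no rule keeps Decision Coach contacts out of the count. The coach-contact part is the more serious because it affects one arm only. It matters little if misreporting is rare (6% to 8% significant at f = 5%) and a good deal if it is not (22% to 49% at f = 20%). These are not error rates of the planned analysis: they assume the misreporting rates, borrow the base rates from other populations, and use a simple test at 54 per arm. Because the two parts pull in opposite directions, neither a positive nor a null H1 result could be read cleanly without the rule.

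**What to change.** Define qualifying help once and use that definition in B.3.6, B.3.8 and B.3.11: AUD medication, behavioural treatment by a non-study provider, or mutual-help, begun after randomisation. Counting from randomisation, not discharge, keeps help that starts in hospital.

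Exclude screening BIs from the primary outcomes, in whatever setting they occur, and report them separately as secondary. Exclude all Decision Coach contacts, in person and by telephone. Apply both exclusions to TLFB and CDW counts, and use the resulting variable as the mediator in B.3.12.

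Interviewers should record all reported help as they do now, with no separate code for coach sessions, since such a code would unblind them. Unblinded data staff then remove coach contacts using the session log.

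The cost is a wording change, a small data-processing step and lower initiation rates in both arms. No extra patients or visits are needed.

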B.3.3. Eligibility criteria for patients' study participation are (1) in a current episode of inpatient medical-surgical care, (2) meet DSM 5 criteria for an AUD (moderate or severe), (3) no specialty addiction treatment or weekly mutual-help group attendance within 60 days prior to the inpatient episode, (4) no restricted access due to infection control requirements (e.g., TB, MRSA, C. diff), (5) no significant cognitive impairment, (6) ongoing access to a cell or landline telephone, (7) at least one contact who will continue to know the patient's contact information, and (8) not having participated in an interview for Aim 1. In FY14, 469 unique patients at VA Palo Alto, and 453 unique patients at VA Ann Arbor, had an inpatient medical-surgical stay, an AUD diagnosis, and

no specialty addiction treatment within the 60 day period preceding the stay. In our HSR&D projects on Veterans in inpatient psychiatry, 14% of potential participants were ineligible due to infection control restrictions, cognitive impairment, lack of ongoing phone access, and/or lack of at least one contact. Excluding up to 15% of inpatients with AUD due to ineligibility leaves 399 and 385 eligible patients per year at VA Palo Alto and VA Ann Arbor, respectively. Of patients who meet eligibility criteria, we expect (based on our current project, achieving a 78% consent rate) that at least 75% will agree to participate - a minimum of 299 patients per year at VA Palo Alto, and 289 patients per year at VA Ann Arbor. Therefore, our plan to recruit the sample of participants over 1.5 years is clearly feasible. Because we are successfully recruiting participants at a similar rate in our ongoing HSR&D project on inpatient detox, we are confident that we will achieve recruitment goals for this study. Although we could enroll patients at a faster rate, we plan to recruit at the proposed pace because a faster rate would overload Decision Coaches providing the intervention, and research assistants conducting intake and follow-up assessments.

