**Substance use and medical outcomes.** We will use the Timeline Follow-Back (TLFB) to assess substance use during the 30 and 90 days preceding baseline. The TLFB is a widely used, standardized, calendar-based retrospective self-report assessment to quantify daily substance use. For alcohol, we will examine the primary outcomes of abstinence, percent of drinking days, and percent of heavy drinking days, i.e.,  $\geq 4$  standard drinks per day for women,  $\geq 5$  for men. The TLFB also measures the most consecutive days of drinking, and most consecutive days abstinent. For the secondary outcome of drug use, we will examine percent using days, most consecutive days of using, and most consecutive days abstinent. The TLFB yields high temporal stability, validity, and agreement between self-reports and biological tests, collateral reports, and official records (from hospitalizations, jail stays). To assess medical status, we will use the Veterans SF-12, a 12-item self-report questionnaire that has been widely used and documented as a reliable and valid measure of the functional effects of illness in VHA patients. SF-12 responses are aggregated into a physical component summary (PCS) score, constituting a primary outcome that reflects overall physical health status. Lower summary scores indicate worse health, and Veterans' SF-12 scores are related predictably to differences in morbidity, healthcare needs, and healthcare expenditures.

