Research assistants, blinded to patients' condition assignment, will collect self-report data by telephone at 3 months, which will be upon completion of the intervention for the group in the DO-MoST condition, and then 6 and 12 months post-baseline. We will use an intent-to-treat design and so will follow patients who do not complete the intervention. Six months is a necessary follow-up point because most (60%-80%) patients treated for AUDs who relapse do so within this interval. Twelve months is a necessary follow-up point because the 6 months preceding that time point continue to be of high risk for relapse. Follow-up assessments will be conducted by telephone because patients may not reside in close geographical proximity to the Palo Alto or Ann Arbor VA. As noted (A.7), we have successfully used telephone interviews to collect follow-up data in HSR&D studies with inpatients. Follow-up interviews will take approximately one hour each. Patients will have the option of completing the interview in shorter sessions, with breaks, due to scheduling needs or fatigue.

We will measure patients' drinking and help preferences using the same measure with the Decision Coach at baseline. We will use the AUDIT-C, DSM 5 for alcohol diagnoses, TLFB, and SF-12 to measure substance use and medical status at follow-ups, supplemented by portions of the ASI. The TLFB (covering the period since the prior interview at each follow-up) will assess the same primary alcohol outcomes (abstinence, percent of drinking days, of heavy drinking days) and other substance use indices assessed at baseline. The ASI will provide recent (past 30 days) alcohol and drug use composite scores. The TLFB and ASI are valid and reliable when given by telephone. We will be able to compute dichotomous scores regarding abstinence from alcohol, drugs, and both alcohol and drugs over the assessed periods. The SF-12 will yield the primary outcome reflecting overall physical health status.

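### Self-reported weeks of help are counted over 3, 3 and 6 months, but the slope model has no term for time covered and names no link (minor)

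*Combined protocol and SAP*

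**What the plan says.** **Schedule and recall (B.3.8).** Interviews are held by telephone at 3, 6 and 12 months. Help is self-reported on the Timeline Follow-Back (TLFB): "treatment types, amounts, and settings) since the previous interview. Primary outcomes will be any use of alcohol help, and duration (weeks) of help". Drinking is recalled in the same way: "The TLFB (covering the period since the prior interview at each follow-up) will assess the same primary alcohol outcomes". The plan will also compute "dichotomous scores regarding abstinence from alcohol, drugs, and both alcohol and drugs over the assessed periods".

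**Baseline (B.3.6 and B.3.3).** The TLFB is used "to assess substance use during the 30 and 90 days preceding baseline". It is described as a "calendar-based retrospective self-report assessment to quantify daily substance use". Eligibility requires "no specialty addiction treatment or weekly mutual-help group attendance within 60 days prior to the inpatient episode", which holds recent help near zero at entry.

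**Model (B.3.11).** Generalized mixed models are fitted over four time points. Each outcome gets a linear trajectory per patient, with the intercept at intake, and average slopes are estimated for each arm. Distribution and link are to be chosen to suit the outcome, with Poisson mentioned for visits and inpatient days. No offset, rate or exposure term appears.

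**Other sources (B.3.10).** VHA care comes from dated Corporate Data Warehouse (CDW) and Fee Basis records, which also serve Hypothesis 1 on entering and staying in treatment.

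**The concern.** The recall windows are stated. What is missing is a common scale for analysis. A total over six months is not comparable with a total over three, yet the slope model treats the values as repeated measurements of one quantity.

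Weeks of help is a primary outcome, and the slope by arm is one of the listed model parameters. If raw totals are used on an identity link, the doubled final window feeds directly into the slope difference between arms. A steady benefit then looks steeper than it is, and a benefit that fades after month 6 looks better maintained. B.3.8 justifies the 12-month interview on the ground that "the 6 months preceding that time point continue to be of high risk for relapse". That reason is about drinking, but the same late interval is the one counted double for help.

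The self-reported measure matters because mutual-help, and non-VA help outside the Fee Basis files, have no other source.

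**Working it through.** The plan gives no figure of its own for this point, so there is none to reproduce.

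**Inputs from the documents.** Interviews at 3, 6 and 12 months (B.3.8); four time points including intake (B.3.11); 78 per arm (B.3.1); follow-up target of at least 70% (B.3.9), so 0.70 × 78 = 54.6, taken as 55 per arm. Help rates, gaps and standard deviations are not given; those below are assumptions.

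**1. Windows.** 3 − 0 = 3, 6 − 3 = 3 and 12 − 6 = 6 months. A missed 6-month interview makes the last window 12 − 3 = 9 months.

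**2. Identity link, four-point slope of the arm gap.** Least-squares slope = Σ(t − 5.25)·gap / Σ(t − 5.25)², with t = 0, 3, 6, 12 and denominator 27.5625 + 5.0625 + 0.5625 + 45.5625 = 78.75. The gap at baseline is 0 by randomisation.

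| True gap (weeks per quarter) | Raw weeks: gaps, slope | Per quarter covered: gaps, slope |
|---|---|---|
| Constant at 1 | 0, 1, 1, 2: 12/78.75 = 0.152 | 0, 1, 1, 1: 5.25/78.75 = 0.067 |
| Halves after month 6 | 0, 1, 1, 1: 5.25/78.75 = 0.067 | 0, 1, 1, 0.5: 1.875/78.75 = 0.024 |
| Stops at month 6 | 0, 1, 1, 0: −1.5/78.75 = −0.019 | identical: −0.019 |

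In raw weeks, a halving benefit has the same slope (0.067) that a constant benefit has once rescaled. The rescaled slope for a constant gap is still not zero, because a straight line is being drawn through a zero baseline.

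**3. Log link.** Take 3 v 4 weeks per quarter, so expected totals are 3, 3, 6 and 4, 4, 8 at months 3, 6 and 12. The ratio is 4/3 at each visit, so the arm-by-time term is 0 with or without an offset. The common slope is 0.0865 per month without an offset (exp(0.0865) = 1.09, about 9% per month) and 0 with one. Adding an equal baseline of 0.25 to 1 week gives an arm-by-time term of 0.0021 to 0.0074 without the offset and 0.0020 to 0.0068 with it.

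**4. Error rate and power of the four-point slope test.** Simulation of 4,000 trials, 55 per arm, baseline 0, usual-care mean 3 weeks per quarter, normal values with patient SD 2.1 and residual SD 2.1, per-patient slopes compared by t-test. Null rejection is 4.3% for raw weeks and 4.3% per quarter covered. Power for the constant 1-week gap is 48% v 41%; repeat runs gave up to 49% v 42%. A benefit that stops at month 6 is detected in about 6% v 8%.

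**5. Yes/no outcomes.** For two 90-day blocks with within-patient correlation r, whole-window abstinence is p² + r·p(1 − p), and any help is 1 − [(1 − p)² + r·p(1 − p)].

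| Assumed 90-day rates | Odds ratio, one block | Two blocks: r = 1 | r = 0.5 | r = 0 |
|---|---|---|---|---|
| Abstinence 60% v 40% | 2.25 | 2.25 | 2.37 | 2.95 |
| Any help 36% v 18% | 2.56 | 2.56 | 2.66 | 2.96 |

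**6. Unequal missed interviews.** A 10-point arm imbalance in missed 6-month interviews, with 50% abstinent per quarter and r = 0, shifts the arm difference by 0.10 × (0.25 − 0.125) = 1.25 points. At r = 1 the shift is 0. The standard error is √(2 × 0.33 × 0.67 / 54.6) = 9 points.

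**The case against.** **The link is left open, and a log link is a natural choice.** Weeks of help is a non-negative count, and B.3.11 promises a model suited to the outcome's distribution. On a log link the arm-by-time distortion all but vanishes. This stands, and it is why the finding is conditional. But choosing a link does not supply an exposure term: the common slope of about 9% per month would remain.

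**Hypothesis 1 asks about more and longer help over the year, not about its time pattern, and the arms share the same windows.** This also stands. A reader might infer that the unequal windows could create a false treatment effect. They do not: null rejection is unchanged when interview completion is equal, and even a marked imbalance in missed interviews moves rates by little against their standard error.

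**Persistence of benefit.** A reader might infer that the plan would badly misjudge whether a benefit lasts. A test of change in the arm gap over months 3 to 12 alone would be distorted heavily, but B.3.11 specifies a slope from intake. On that slope a benefit that stops at month 6 has the same expected value either way and is hardly detectable either way.

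**VHA care is dated.** CDW and Fee Basis records are unaffected, so the exposed part is self-report, chiefly mutual-help and non-VA help outside Fee Basis.

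**The simulation is crude.** Normal weeks with mean 3 and total SD 2.97 put about 16% of quarterly values below zero. The power figures are indicative only; the slopes in step 2 are exact arithmetic and do not depend on them.

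**Conclusion.** The point holds as a minor one. Self-reported weeks of help, a primary outcome, is collected over windows of 3, 3 and 6 months and enters a slope model with no adjustment for time covered. On an identity link with raw totals, the arm slope difference is 0.152 instead of 0.067 weeks per month for a constant gap of 1 week per quarter, and 0.067 instead of 0.024 if that gap halves after month 6. On a log link only the common time slope is materially affected. If time is fitted as a factor, the common shift is absorbed, but an identity-link contrast at month 12 is still on a six-month scale.

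The effect on any help is nil to moderate. Abstinence is affected to a similar degree, and only if it is scored over the whole TLFB period. The wording in B.3.8 suggests this, but a 90-day score as at baseline is also possible. Percent of drinking days and of heavy drinking days are already scaled to their window.

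The documents do not support saying that the recall windows are unstated, that type I error is inflated, or that the trial cannot answer Hypothesis 1. The sizes rest on the assumed gaps, rates and correlations shown in the working.

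**What to change.** 1. Name the link for self-reported weeks of help. Analyse it as weeks per week covered, or in a count model with a log(time covered) offset.
2. Score any help and abstinence on equal 90-day windows from the TLFB calendar, preferably by splitting months 6 to 12 into two blocks so that no days are lost. Any help over the whole year can still be reported as one yes/no result.
3. If an interview is missed, fill its window from the next interview's calendar and flag it. Cut VHA records on the same windows.

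**Cost.** Plan wording and derivation code. Power for the four-point slope test falls slightly (about 42% against 49% in the assumed scenario), partly because the higher figure comes from counting the last period double. Splitting the last window adds a time point that does not match the SF-12 and ASI visits, and filled windows involve longer recall. Daily data are stated for substance use; for help the documents mention type, amount and setting, so it is assumed that the calendar dates help. If it does not, the interview form must record start and stop dates.

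**What it does not fix.** Rescaling leaves the slope that arises from fitting a straight line through a near-zero baseline (0.067 weeks per month for a constant gap).
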